#### C. Hypothesis/specific aims:

The aims of this pilot, randomized controlled trial are:

*Aim 1:* To assess the feasibility of a full-scale effectiveness trial comparing PICCs to LPCs in hospitalized pediatric patients in need of non-central, medium-term vascular access (5-14 days anticipated need). *Hypothesis:* Feasibility of a full-scale effectiveness trial will be established by demonstrating that > 70% of eligible patients agree to enrollment and randomization, > 80% of randomized patients receive the assigned intervention, > 80% of providers involved find the study acceptable, and < 5% of data are missing.

*Aim 2*: To identify a population in which a LPC is a safe and effective alternative to a PICC for vascular access in hospitalized pediatric patients age > 2 years, in need of non-central, medium-term access. *Hypothesis:* We hypothesize that LPCs are non-inferior to PICCs for delivery of peripherally compatible infusate needed for 5-14 days in hospitalized pediatric patients. We plan to determine the time-to-removal of the vascular access device, both secondary to completion of therapy and secondary to complications. Safety will be assessed by measuring complication rate (e.g., VTE, CLABSI, occlusion, dislodgement, phlebitis). Cross over rate will be closely monitored as well.

*Aim 3:* To engage patients and families as advisors in vascular access device selection. We will describe the patient and family experience with device placement and maintenance as well as perceived patient and parent insertion-related and sedation-related distress.

D. Background, significance, and rationale (including description of preliminary studies and any results):

Many hospitalized children require a vascular access device (VAD) for delivery of life saving interventions such as intravenous fluids and antibiotics.[1] With the broad range of VADs available, and their different profile of complications,[2] it is essential that clinicians have access to rigorous evidence to guide the selection of the most appropriate VAD. Appropriate VAD selection results in treatment efficiency and a decrease in catheter-related complications.[1] The problem is, even the most current and comprehensive guideline for VAD selection published in 2020, the Michigan Appropriateness Guide for Intravenous

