#### E. Design and methods (including experimental design, technical details and laboratory methodology):

#### Study design:

Randomized clinical trial. We propose a parallel group, pragmatic randomized non-inferiority pilot trial design (*arm 1* and *arm 2*) (**Figure 1 below**) assessing the feasibility of a full-scale effectiveness trial comparing PICCs to LPCs for non-central, medium-term vascular access (5-14 days) in pediatrics.

Mixed methods (qualitative and quantitative data) will be used to determine patient/family experience.

**Setting and sample:** This single center pilot study will take place at Children's Wisconsin main hospital in Milwaukee. We plan to use convenience sampling, enrolling Monday through Friday 8-5pm during the one-year timeline.

Inclusion criteria: patients age 2 to 17 years admitted to Children's Wisconsin and requesting placement of a PICC () for: (1) anticipated length of intravenous treatment of 5-14 days, (2) planning peripherally compatible infusates [28] (3) VAD not needed at discharge.

Exclusion criteria: non-English-speaking family, active bacteremia or VTE at site where device would be placed, urgent need of vascular access (within 4 hours), another central venous catheter already in place, device needed for any intervention requiring central access such as medications that cannot be given peripherally OR central monitoring. To be included in the study, the treating attending physician will need to give approval for participation and randomization.

Inclusion/Exclusion criteria for guardian participation in the semi-structured interviews: > 18 years old, English speaking.

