#### Interventions:

After recruitment and consent, patients will be 1:1 randomized to receive:

1. **PICC:** Bard 3fr, 4fr or 6fr; Cook 4fr; or Medcomp 1.9fr and 2.6fr. (type and size to be selected based on interventional radiology standard protocol)

2. LPC: Bard Powerglide 8 cm, 20G and 22G. (size to be selected based on patient size)

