#### / Study-wide (if applicable): N/A

**Describe what are these numbers are based on:** In a prior study, we showed that 139 PICCs over a one-year period could have been avoided at our local hospital as they (1) delivered peripherally-compatible infusates, (2) stayed in for < 14 days and (3) were removed prior to discharge. This is the population that we target for our study. For this pilot trial, we plan to enroll 35 patients in each randomized study group (35 participants in arm 1 and 35 participants in arm 2 of the study). The study is not powered to detect statistical significance, but rather to assess the feasibility of this study protocol for a larger full-scale effectiveness trial and provide baseline estimates for the sample size calculations. With a **sample size of 60 or more** patient subjects, we will be able to estimate a participation rate of 70% (eligible patients agree to enrollment and randomization) within a 95% confidence interval of +/- 12%.

The decision to include up to 70 adult guardians in the semi-structured interview portion was made to reach thematic saturation in qualitative analysis. Selection criteria for the interviews will be based on the number needed to meet qualitative saturation of data. All parents who enroll in the study will be asked to participate in the structured interview until qualitative thematic saturation is met. As such, selection criteria in effect will be based on chronology of participation in the study and number of interviews obtained from participants who agreed.

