#### D. Describe procedures to be employed in analyzing data (including a power analysis):

Quantitative. Study data will be collected using REDCap. Feasibility outcomes will be collected from (1) screening logs maintained by the study team (rate of enrollment, assigned intervention), (2) ease/difficulty of VAD placement (scale 0=worse to 10=best) to determine VAD acceptability, and (3) REDCap datasheet for assessing missed data. Patient demographics (age, gender, race/ethnicity), clinical factors (reason for admission, co-morbidities, reason for PICC/LPC request, therapy to be infused, requesting service, hospital floor), VAD data (VAD type and size placed, insertion site/vessel, sedation, number of attempts, additional VADs), effectiveness data (time-to-removal of VAD, prolonged NPO, number of lab draws from VAD, number of non-VAD blood draws) and complications requiring medical intervention will be collected using the EMR and daily (Monday-Friday) check-ins with the bedside nurse. Procedural pain with non-sedated VAD placement will be assessed in patients age > 5 years by the RC within 24 hours of insertion using the Faces Pain Score (FPS) or the 0-10 pain scale depending on the developmental age of the patient. Patient/parent anxiety and overall experience with VAD placement will be assessed on a 0-10 scale (0= lowest, 10=highest) and using the short State-trait anxiety inventory (STAI) that is validated in children 5 and older.

Descriptive statistics will be used to report feasibility outcomes and explore clinical factors (see above). Cross over rate will be calculated as the proportion of the number of subjects who crosses from the randomized arm/line to a different arm/line. The exact Clopper-Pearson 95% confidence interval will be generated. Time-to-device removal for all reasons will be compared using a t-test. Non-inferiority of LPCs to PICCs will be demonstrated if the 95% confidence interval of the mean difference lies above -1 (non-inferiority margin: 1 day). The remaining outcomes will be compared using Chi-square test or Fisher's exact for categorical variables and t-test or Mann-Whitney-Wilcoxon test for continuous variables. Where necessary for parametric assumptions, appropriate transformations will be employed. Non-parametric tests will be used where parametric assumptions are not satisfied. Logistic regression or general linear model will be performed to control the potential confounders.

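### Aim 2 splits time to removal by cause, but the analysis section has no competing-risk method, so a cause-specific time would describe only children selected by their outcome and say almost nothing about how often a device fails

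*Combined protocol and SAP*

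**What the plan says.** Section 1, C (Aim 2) sets the outcome by cause of removal: "We plan to determine the time-to-removal of the vascular access device, both secondary to completion of therapy and secondary to complications".

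Section 6, D gives the methods:
- All-cause time: "Time-to-device removal for all reasons will be compared using a t-test". Non-inferiority is judged on this outcome alone, by whether the "95% confidence interval of the mean difference lies above -1 (non-inferiority margin: 1 day").
- Everything else: "The remaining outcomes will be compared using Chi-square test or Fisher's exact for categorical variables and t-test or Mann-Whitney-Wilcoxon test for continuous variables".
- Adjustment: "Logistic regression or general linear model will be performed to control the potential confounders".

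No survival or competing-risk method is named. No rule says what value a child contributes to one cause when the device came out for the other. The cause-split times are not mentioned again in Section 6, D.

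Failure frequency is covered elsewhere. Complication rate is the Aim 2 safety outcome. Section 6, B plans looks at complication, catheter failure and cross-over rates after 20 and 40 enrolments. Section 6, C has a stopping rule on catheter failure.

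**The concern.** Completion and complication are competing events. A child whose therapy finished has no time to complication removal, and a child whose catheter failed has no time to completion removal. A t-test or rank test needs one value per child, so applied to these times it can only compare failures with failures, or completers with completers. Membership of those groups is decided after randomization by the outcome itself, so the comparison is no longer between the randomized arms.

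The number obtained also answers the wrong question. Time to failure among failures reflects when failures happen within a short course, not how many there are. At stake is the cause-specific estimate that Aim 2 promises. Section 6, D says that the pilot is to supply baseline estimates for sizing the full-scale trial, and that trial needs the proportions failing and completing by a given day.

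**Working it through.** **The plan's own figures.** None is given for time to removal. The only precision figure is for a 70% participation rate with 60 subjects: 1.96 × √(0.7 × 0.3/60) = 11.6 points, which reproduces the stated ±12. It does not bear on this point.

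**Inputs from the documents**
- 35 per arm (Section 3, A: "35 participants in arm 1 and 35 participants in arm 2 of the study"), allocated 1:1.
- Need: "anticipated length of intravenous treatment of 5-14 days" (Section 1, E).
- PICC failure 10-20%, from 80-90% completion of therapy (Section 8, E, Risk Level 2); 15% is the midpoint.
- LPC failure (Section 1, Preliminary work and results). In the first series 11 of 20 remained to completion, so 9/20 = 45% did not; the listed occlusions and dislodgements are 2 + 5 = 7, or 35%. In the later series, 9 of 43 = 21% were removed for complications.

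**Assumptions.** Need D is uniform on 5-14 days, failure time T has constant daily hazard h, the two are independent, and the device is removed at min(T, D).

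**Formulas**
- Failure proportion: p = 1 − (e^(−5h) − e^(−14h))/(9h). Solving gives h = 0.0172 for 15%, 0.0250 for 21%, 0.0461 for 35% and 0.0644 for 45%.
- Mean time among failures: (1/p) × average over D of [1 − e^(−hD)(1 + hD)]/h.
- Mean time among completers: average of D·e^(−hD), divided by (1 − p).

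**Results, LPC v PICC.** The percentages of significant trials come from simulating trials of 35 v 35.

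| Failure, LPC v PICC | Mean days among failures | Mean days among completers | t-test among failures significant | Fisher on failure, all children | All-cause difference in days | All-cause t-test significant |
|---|---|---|---|---|---|---|
| 45% v 15% | 4.4 v 4.9 | 9.1 v 9.4 | 6-7% | 73% | −1.7 | 55% |
| 35% v 15% | 4.6 v 4.9 | 9.2 v 9.4 | 5-6% | 38% | −1.1 | 27% |
| 21% v 15% | 4.8 v 4.9 | 9.3 v 9.4 | 5% | 6% | −0.3 | 7% |

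The t-test among failures stays near its 5% false-positive rate in every row. In the first row the LPC mean among failures is the longer one in about 39% of trials.

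**Sensitivity**
- Weibull shapes 0.7 and 1.5, at 45% v 15% and 30% v 10%: failure-time differences are 0.2 to 0.5 days and the t-tests on the split times are significant in 6-10% of trials.
- Unbounded need (exponential, mean 8 days): mean time among failures is 8 × (1 − p), so 8 × 0.55 = 4.4 v 8 × 0.85 = 6.8 days at 45% v 15%, a gap of 2.4 days. The near-equality of the means therefore depends on bounded need, which is the eligibility criterion. Even then the t-test among failures is significant in only about 6%.

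**What cumulative incidence gives.** At 45% v 15%, removal for complication is 35% v 11% by day 7 and 45% v 15% by day 14. Every randomized child is in the denominator. The approximate 95% half-width for the day-14 difference is 1.96 × √(0.45 × 0.55/35 + 0.15 × 0.85/35) = 20 points.

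**The case against.** The strongest reply is that no test of these times is stated. Aim 2 says only that they will be determined, and the single named comparison is of removal for all reasons. The split may be meant descriptively, or the two reasons in Aim 2 may simply be the all-reasons outcome spelled out. This stands: applying a t-test or rank test to the split times is an inference from the remaining-outcomes sentence. It does not remove the point, because a descriptive mean within one removal type has the same selection problem, and if no analysis is intended then a stated Aim 2 outcome has none.

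A reader might infer that the trial could miss a device that fails three times as often. The documents do not support that. The complication-rate comparison, the failure-rate looks and stopping rule, and the all-cause t-test all respond to failure frequency. In the 45% v 15% scenario the all-cause difference is −1.7 days and the chance of declaring non-inferiority is about 0.2%.

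A reader might also take the 6-7% against 73% contrast as the size of the problem. It belongs to the first LPC series only. With the later series (21%) no method distinguishes the arms at this sample size, and the study makes no power claim. Nor do the documents propose a Kaplan-Meier failure curve with completion censored, so that is not a fault to lay at the plan's door.

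**Conclusion.** The point holds as one of estimation, confined to the cause-split times in Aim 2. Any mean or test of time within one removal type compares children selected after randomization and is nearly blind to failure frequency: differences of 0.1 to 0.5 days across LPC failure of 21% to 45% against 15% for PICC, with significance in about 5-7% of trials. This rests on uniform 5-14 day need, a roughly constant hazard and failure independent of need. The selection problem itself needs none of these.

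It does not undermine the feasibility aim, the all-cause non-inferiority comparison or the safety monitoring. It is worth correcting because the pilot is meant to feed the full-scale design, and a cause-specific time would be a misleading input. All-cause time cannot stand in for it, since early success and early failure both shorten it.

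**What to change.** In Section 6, D, state that time to removal by cause will be reported as cumulative incidence (Aalen-Johansen) of (a) removal for complication and (b) removal at completion of therapy. Treat each as a competing event for the other, include all randomized children by assigned arm, and give between-arm differences with 95% CIs at day 7 and day 14. State that any mean or median time within one removal type is descriptive only and will not be tested between arms. Say also how a removal for neither reason is classed; in the later LPC series 43 − 30 − 9 = 4 devices fall under neither heading.

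The cost is wording and slightly more analysis. It needs only the removal date and reason, which Aim 2 already requires, and no extra children. The intervals will be wide, about ±20 points at 35 per arm, and there will be two curves per arm instead of one mean.

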#### Need for feasible alternatives for medium-term non-central vascular access

To reduce inappropriate PICC utilization, feasible alternatives for medium-term, non-central venous access need to be identified and tested. Long Peripheral Catheters (LPCs, see **Table 1**) have been recently adopted by some adult hospitals for short and medium-term venous access (<14 days) due to potential for fewer complications compared to PICCs.[17,18] Use of LPCs instead of PICCs for medium-term vascular access

	PICC End of Catheler	LPC End of Catheter
Tip of the catheter	Central vein (e.g., superior vena cava)	Peripheral vein (e.g., basilic vein)
Type of infusate delivered	Vesicant and non-vesicant medications/solutions (e.g., chemotherapy)	Only non-vesicant medications/solutions (e.g., antibiotics)
Ultrasound guidance used	Yes	Yes
XR for tip location used	Yes	No
Sedation used	Commonly	No
Dwell-time	> 30 days	< 30 days
Used outside of the hospital setting	Yes	Variable (no at CW)
Blood-drawing abilities	Yes	Yes (but unclear for how long)
Complications	CLABSI and VTE Occlusion, dislodgement, leaking, phlebitis	Occlusion, dislodgment, leaking, phlebitis, infiltration
Estimated cost of supplies, labor, imaging (Chenoweth et al)	\$590	\$73

Table 1: PICC versus LPC - Similarities and Differences

would benefit patients and healthcare organizations by reducing need for sedation [19] and lowering cost.[14,20] (Table 1) Unfortunately, there is a scarcity of literature evaluating the effectiveness of LPCs in pediatrics. The few published studies in this population generally describe program development and summarize retrospective data.[14,21,22] Prior studies are limited by small sample size [23–25], with poor generalization outside of specific populations, e.g., neonatal intensive care unit (NICU) [14,26] and cystic fibrosis [19,21,23]. Despite the low quality and quantity of published data, a few themes emerge. First, LPCs have longer dwell-time than the classic peripheral intravenous catheters (9.2+- 6 day vs 3.2+-2.1 days respectively; p<0.0001)[25], with an average LPC dwell-time of 4-12

days,[14,21–24,26,27] supporting their use for medium-term vascular access. Second, LPCs tend to have fewer significant complications compared to PICCs, aligning with findings in the adult literature. In one study, PICCs were associated with more complications during placement while LPCs had more complications during use.[22] A second study, a retrospective review of neonatal cases, showed that LPCs had no lifethreatening complications while PICCs were associated with 4 life-threatening events during the study Form Version Date: 02/24/2020 CW Protocol Summary Page 3 of 30

period.[14] Both studies were completed using retrospective analysis of electronic medical records (EMR), so more rigorous study designs comparing PICCs to LPCs are still needed. The feasibility of a randomized clinical trial comparing PICCs to LPCs in children with cystic fibrosis was proven possible in an Australian pediatric center, with a reduction of general anesthesia use for VAD placement (69% in PICCs vs 10% in LPCs).[19]

#### Preliminary work and results

We are one of the first few pediatric hospitals in the United States to implement and describe the development of an LPC program.[6] The LPC program was introduced at Children's Wisconsin (CW) in 2019 and was subsequently initiated in the intensive care units. In October 2021 the program expanded to the rest of the hospital. Our ability to place LPCs in hospitalized children gives us a significant advantage in obtaining high quality evidence regarding LPC use in pediatrics. In our initial test group of 20 successfully placed LPCs, there were no major complications such as VTE or CLABSI (*Table 2*). We did identify a 25% dislodgement rate that we are working to reduce by improving the LPC securement.

LPCs inserted (n)	20
Patients (n)	19
Age (years) median (IQR)	11 (7-15)
Male, n (%)	9 (45%)
Location, n (%)	
Acute Care unit	9 (45%)
Intensive Care unit	11 (55%)
Service, n (%)	
Critical Care	7 (35%)
Gastroenterology	6 (30%)
Hospital Medicine	4 (20%)
Oncology	3 (15%)
Anatomic Site, n (%)	
Cephalic vein	7 (35%)
Basilic vein	12 (60%)
Brachial vein	1 (5%)
Number of insertion attempts, n (%)	
1 attempt	19 (95%)
2 attempts	1 (5%)
Catheter size	
22 gauge	10 (50%)
20 gauge	10 (50%)
PIV insertion attempts prior to LPC.*n (%)	
0 attempts	12 (60%)
1 attempt	4 (20%)
2 attempts	3 (15%)
3 attempts	1(5%)
LPC Duration, days, median (IQR)	5.5 (1-9)
Remained until therapy completion, n (%)	11 (55%)
Complications, n (% )	
Occlusion	2 (10%)
Dislodgement	5 (25%)
Phlebitis	0 (0%)
Venous Thromboembolism	0 (0%)
Central Line Associated Blood Stream	0 (0%)
Infections	

Since the initial pilot of the LPC program, 43 LPCs have been placed at CW as standard of care (up until November 2021, see figure below). All LPCs were placed in the upper extremity (77% in the upper arm); 88% were placed in the PICU. The median (IQR) dwell-time was 6 (3-11) days; 14% remained in for > 14 days (max dwell-time 41 days), 19% for 7-14 days, and 58% for  $\leq$ 7 days. Reason for removal was "no longer medically needed" in 70% (n=30) of the LPCs and complications in 21% (n=9). Most frequent complication was occlusion (n=3) and infiltration (n=2). These complications are similar to those of a peripheral IV. No clots or line infections identified.

#### E. Design and methods (including experimental design, technical details and laboratory methodology):

#### Study design:

Randomized clinical trial. We propose a parallel group, pragmatic randomized non-inferiority pilot trial design (*arm 1* and *arm 2*) (**Figure 1 below**) assessing the feasibility of a full-scale effectiveness trial comparing PICCs to LPCs for non-central, medium-term vascular access (5-14 days) in pediatrics.

Mixed methods (qualitative and quantitative data) will be used to determine patient/family experience.

**Setting and sample:** This single center pilot study will take place at Children's Wisconsin main hospital in Milwaukee. We plan to use convenience sampling, enrolling Monday through Friday 8-5pm during the one-year timeline.

Inclusion criteria: patients age 2 to 17 years admitted to Children's Wisconsin and requesting placement of a PICC () for: (1) anticipated length of intravenous treatment of 5-14 days, (2) planning peripherally compatible infusates [28] (3) VAD not needed at discharge.

Exclusion criteria: non-English-speaking family, active bacteremia or VTE at site where device would be placed, urgent need of vascular access (within 4 hours), another central venous catheter already in place, device needed for any intervention requiring central access such as medications that cannot be given peripherally OR central monitoring. To be included in the study, the treating attending physician will need to give approval for participation and randomization.

Inclusion/Exclusion criteria for guardian participation in the semi-structured interviews: > 18 years old, English speaking.

